## **Statistics**

### **Sample Size Considerations:**

Calculations for the estimated sample size were completed using a formula for calculation of dichotomous response variables with two independent samples. We assumed  $\alpha = 0.05$  (accepted standard value), power  $(1 - \beta) = 0.80$ , and that 30% of patients in the control group would see their PCP within 30-days. This estimate of 30-day follow-up is taken directly from recent administrative data from Alberta. The sample size was therefore calculated to detect a 30% absolute difference in 30-day follow-up (30% of the standard-care vs. 60% of enhanced care groups). In addition, we used 1-tailed estimates due to the assumption that the intervention will not **decrease** the follow-up of patients with COPD. The total sample size was estimated at 98 (49/group) patients; however, if we assume ~10% attrition (see previous COPD study), the total sample size is estimated at 110 patients.

**Recruitment plan:**

We have full-time research staff nurses at the UAH (coverage 16 hours/day; 08:00-24:00 M-F; 10:00-18:00 S&S) and at the NECHC (8 hours/ day; 10:00-18:00). We will increase our coverage if the numbers indicate the need to do so. We anticipate 5/month at the UAH and 4/month at the NECHC. Approximately one year of enrolment (February 2010-March 2011) should provide the numbers required for this study.

**Principal analysis of the primary outcome measure:**

The final analysis will be performed on an "intention to treat" basis. Using this approach, patients will be included in the analysis according to the group to which they were randomized. Baseline characteristics in the two treatment arms will be compared using univariate descriptive statistics. The principal analysis of 30-day relapse will be done using an unadjusted  $\chi^2$  comparing the proportion of events in each treatment group. A logistic regression procedure will be employed to adjust raw relapse proportions using significant co-variates (such as patient use of inhaled steroids, current smoking status, etc) which may influence outcomes

We chose the proportion of PCP visits within 30 days as a primary outcome measure rather than survival time to relapse. We believe that it is more relevant to both patients and physicians to know if the enhanced intervention will stimulate a PCP visit rather than examining relapse (which may be affected by age, severity, type of treatment received, smoking status, etc). Therefore, unadjusted  $\chi^2$  followed by logistic regression procedures were chosen over log-rank tests followed by Cox proportional hazards modelling. Both alternative analytic approaches mentioned will still be performed and reported.

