**Exclusion:**

Patients presenting for prescription renewal;

Patients who require hospitalization;

Patients who **do not** have a primary care physician or patients for whom a family physician cannot be found;

Patients who have already been enrolled in the study;

Patients with a ED physician-diagnosis of primary asthma, pneumonia, HIV/AIDS, immuno-compromise, or life expectancy of < 90 days.

Patients who, in the opinion of the investigator, should be excluded.

Using concealment of allocation, patients will be randomized using computerized random numbers tables to control and intervention groups. Randomization will be in a 1:1 distribution between the control and intervention group.

Upon enrollment into the study, basic information regarding the patient and their disease status will be collected. An ED chart review will be completed to document ED care. **We will complete the COPD Assessment Test (CAT), a**

**new questionnaire for people with COPD. It is designed to measure the impact of COPD on a person's life and is freely available on the internet ([www.catesonline.org](http://www.catesonline.org)). See Appendix 6 for the complete set of information to be collected.**

All patients enrolled in the study will be discharged home with a standardized protocol for the outpatient management of the AECOPD (**Appendix 5**). This will include a standardized length and dose of both oral corticosteroids (oral prednisone 50 mg once daily X 10 days) and antibiotics (oral Doxycycline 100 mg twice daily X 5 days or Levofloxacin 750 mg once daily X 5 days). The dosage and length of therapy is based on current standards and recommendations outlined in the CTS 2007 (updated 2008) consensus guidelines. The standardized medications will be provided for the patient at no cost to the patient themselves by the Central Research Pharmacy at the University of Alberta Hospital).

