**Principal analysis of the secondary outcome measure:**

All secondary outcome measures will be assessed at 30 days and 90 days and will be analysed using an "intention to treat" analysis. Patients will be contacted to see if they have had an urgent visit (to ED or their PCP). If they describe a relapse (an unscheduled visit for worsening COPD), then we will obtain further information from their medical records and/or treating physician. Those patients who relapse within the first 30 days of the trial will have measurements of oxygenation, airflow obstruction, dyspnea, and quality-of-life done on the day of relapse (either from the family physician or the EDs where they attend). These values will be counted as the last day values for purposes of the analysis (i.e., endpoint analysis, with the last observation carried forward).

Continuous outcome measures including absolute and percent changes in FEV1, oxygen saturation, Transitional Dyspnea Index scores, and changes from Day 1 to Day 30 in the scores of the four components of the Chronic Respiratory Questionnaire will be analysed using either parametric procedures (independent t tests) initially, or with non-parametric methods (Wilcoxon Rank Sum) if the data is not normally distributed. At 90 days, the proportion of patients who achieve

compliance with recommendations (for LAAC, LABA/ICS combinations, and rehabilitation referral), relapse and are hospitalized will be compared using unadjusted  $\chi^2$  tests followed by logistic regression procedures. Survival analyses (log-rank tests followed by Cox proportional hazards modelling) will be used to compare time to relapse.

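### The adjusted logistic analysis takes 'significant' covariates from an open list, so several adjusted results are permitted; a small set should be named in advance

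*Combined protocol and SAP*

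**What the plan says.** In the section on the principal analysis of the primary outcome, the lead test is unadjusted: "The principal analysis of 30-day relapse will be done using an unadjusted" chi-square. A logistic regression then serves to "adjust raw relapse proportions using significant co-variates (such as patient use of inhaled steroids, current smoking status, etc". The sentence adds that such covariates may affect outcomes, but gives no closed list, test, threshold or cap.

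The same section says "Baseline characteristics in the two treatment arms will be compared using univariate descriptive statistics", without linking that comparison to covariate choice. It goes on: "We chose the proportion of PCP visits within 30 days as a primary outcome measure rather than survival time to relapse". It explains that chi-square "followed by logistic regression procedures were chosen over log-rank tests followed by Cox proportional hazards modelling". The regression is therefore a planned second step, in support of the chi-square test.

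For the 90-day proportions (compliance with recommendations, relapse, hospitalisation), the section on the secondary outcomes plans chi-square "tests followed by logistic regression procedures". It names no covariates there and does not say whether the significance rule carries over.

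On data available at baseline, the enrolment text under the exclusion criteria says "We will complete the COPD Assessment Test (CAT".

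**The concern.** In a statistics section, 'significant' most naturally means statistically significant in this trial's data. The text does not say whether that means associated with the outcome, retained by a stepwise procedure, or different between arms at baseline. Each reading can lead to a different model, and the choice can be made after the results are known.

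The reader would then see a raw comparison beside an adjusted one whose covariates were settled late. Its standard error would take no account of how they were chosen. With fewer than 100 analysed patients, significance tests are also a weak way to find out which covariates matter. What is at stake is the credibility of the adjusted estimate, not the principal test.

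**Working it through.** **1. The plan's own sample size.** Inputs from Sample Size Considerations: "30% of the standard-care vs. 60% of enhanced care groups", α = 0.05, power 0.80; allocation is 1:1. The mean rate is 0.45 and the difference d is 0.30.

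n per group = [z_α√(2 × 0.45 × 0.55) + z_β√(0.30 × 0.70 + 0.60 × 0.40)]² / d²

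- Two-sided: [1.960 × 0.7036 + 0.842 × 0.6708]² / 0.09 ≈ 42.0.
- With continuity correction: (n/4)[1 + √(1 + 4/(nd))]² = (42.0/4)[1 + √(1 + 4/12.6)]² ≈ 48.4, so 49 per group and 98 in total, as stated.
- The one-sided calculation that the text describes gives 33 per group, or 40 with correction. That is a separate matter and does not affect this point.
- Attrition: 98/0.90 = 108.9, close to the stated 110.

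**2. Information for the model.** Expected PCP-visit events are 49 × 0.30 + 49 × 0.60 = 14.7 + 29.4 ≈ 44. Arm plus four covariates gives 44/5 ≈ 9 events per parameter. This count is for 30-day PCP visits. The quoted sentence speaks of relapse, for which the documents give no rate.

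**3. Comparing the permitted rules.** Simulation with n = 98, 3,000 trials per scenario and a two-sided 5% Wald test. Assumptions not in the documents: 4 or 8 independent binary candidates at 50% prevalence, two of them prognostic with log odds ratio (OR) 0, 0.7 or 1.4. Selection used p < 0.05. Power and SD/SE are at 30% v 60%; type I error is at 30% v 30%. SD/SE is the true standard deviation of the estimate over the mean model standard error. Power ranges are over the two candidate counts; the last two columns are over all scenarios.

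| Rule | Power, log OR 0.7 | Power, log OR 1.4 | SD/SE | Type I error |
|---|---|---|---|---|
| Fixed prognostic pair | 86.8–88.7% | 90.6–91.3% | 1.02–1.05 | 4.5–5.1% |
| Univariate, on outcome | 85.3–87.2% | 89.6–90.1% | 1.01–1.05 | 4.5–5.1% |
| Backward elimination | 86.3–88.1% | 90.3–91.2% | 1.03–1.09 | 4.7–5.9% |
| Baseline imbalance | 85.3–87.5% | 86.5–87.2% | 0.99–1.01 | 4.0–5.2% |
| Most favourable of five models | – | – | – | 5.7–9.5% |

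The five models are unadjusted, fixed pair, univariate, backward, and all candidates. Monte Carlo 95% error is about ±1.3 points on power and ±0.8 on type I error, so the smallest differences are within noise.

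- Power: with prognostic covariates, outcome-based selection costs about 0 to 1.5 points against the fixed pair. Imbalance-based selection costs about 1 to 4 points; the largest gap is 90.6 − 86.5 = 4.1. With log OR 0 there is no consistent loss (fixed pair 85.5–85.8%, selection 84.9–87.0%).
- Uncertainty: within scenarios, backward elimination has an SD/SE ratio about 0.01 to 0.05 above the fixed pair. Univariate and imbalance selection show no such excess.

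**4. Sensitivity to the assumptions.** A second simulation used ten standard normal candidates, four prognostic (log ORs 0.8, 0.6, 0.6, 0.5), and 5,000 trials.

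- Power: fixed set 92.5%, univariate 89.6%, backward 91.7%, unadjusted 86.2%.
- SD/SE: 1.04–1.07 for the fixed set and for univariate selection, 1.11–1.14 for backward elimination.
- Type I error: fixed 4.9%, univariate 4.6%, backward 5.9%, and 7.7% for the most favourable of unadjusted, univariate and backward.
- Univariate and backward selection chose different covariates in 58–69% of trials.

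A further run gave type I error of 4.7% for both univariate selection and the fixed set, with SD/SE of 1.06 and 1.07. The fixed set's power advantage (92% v 90%) appeared only when it was exactly the prognostic set. It vanished or reversed when the set was half right or wrong.

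**5. The 90-day models.** No hospitalisation rate is given. Assumed rates of 5%, 10% and 20% of 98 give 4.9, 9.8 and 19.6 events. For arm plus four covariates that is about 1.0, 2.0 and 3.9 events per parameter, well below the 9 in step 2.

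**The case against.** The strongest reply is that the plan commits to no selection algorithm. 'Significant' could mean important: two clinical examples are given in advance and tied to possible influence on outcomes. A reader might infer that the protocol fixes a p-value rule, but the text does not go that far. This stands, and it changes the nature of the defect: the model is under-specified, and no particular algorithm can be charged to the plan. It does not remove the point, because even the loose reading leaves the list open.

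A reader might also infer that choosing covariates by significance always loses power and understates uncertainty. The calculations do not support that. Univariate selection showed no clear type I or standard-error penalty. The power loss needs prognostic covariates, and the fixed sets compared above were prognostic by construction, knowledge that no trial has. The covariate effects are assumptions throughout.

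The 5.7–9.5% range describes an analyst who reports whichever model looks best. The plan does not propose this; its wording only fails to prevent it.

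Finally, the event count and simulations use PCP-visit rates, whereas the quoted sentence concerns relapse. They are relevant because the sample size and the stated choice of primary outcome rest on 30-day PCP visits. No size can be given for a relapse model.

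**Conclusion.** The point holds as one about an open, data-dependent adjusted analysis. The wording permits several selection rules, and these can give different adjusted treatment effects. Under the assumed scenarios, type I error reaches 5.7–9.5% if the most favourable model is reported. Backward elimination makes the standard error too small by a few per cent more than a fixed set does. The power cost is at most about 4 points, and that only for selection on baseline imbalance with strong covariates.

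A reader might infer that the trial's main result is compromised. It is not: the principal test is an unadjusted chi-square, and neither it nor the sample size depends on covariate choice. Nor do the documents show that the significance rule is reused at 90 days; they show only that no covariates are named there. This is a change worth making to a supportive analysis.

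**What to change.** Replace 'significant co-variates' with a small set fixed before outcomes are seen by arm and included whatever its p-values. For the 30-day PCP-visit model, one workable set is site (the two emergency departments), current smoking, inhaled steroid use at baseline and baseline CAT score. Inhaled steroid use is the plan's own example, but the appendix listing the enrolment data is not in the text reviewed, so confirm that it is recorded at enrolment. State that the sentence applies to PCP visits, so that model and outcome agree.

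Name the set for the 90-day logistic models in advance as well. Give the order in which covariates are dropped when an outcome such as hospitalisation has few events, and the event count that triggers this. The four-covariate set should not be carried over unchanged. Label any other adjusted model exploratory.

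The cost is two or three sentences, with no extra patients and, subject to the check above, no extra data. The downside is that if the named covariates are not prognostic, the adjusted analysis gains no power and may lose slightly. With log OR 0 in step 3, the fixed pair gave 85.8% and 85.5%, against 87.0% and 86.2% unadjusted.

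### An optional gain in precision: a PCP appointment booked before randomisation probably predicts follow-up, but the primary comparison makes no use of it

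*Combined protocol and SAP*

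**What the plan says.** Under Principal analysis of the primary outcome measure, the proportion of patients with a PCP visit within 30 days is the primary outcome. The stated reason is that patients and physicians would rather have the answer "to know if the enhanced intervention will stimulate a PCP visit rather than examining relapse". The planned analysis is a chi-square without adjustment, followed by logistic regression. The covariates given for the regression are examples, "such as patient use of inhaled steroids, current smoking status, etc", and the sentence that names them is about adjusting relapse proportions. The next paragraph lists smoking status among the things that may affect relapse.

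Sample Size Considerations assumes that "30% of patients in the control group would see their PCP within 30-days" and plans to detect "30% of the standard-care vs. 60% of enhanced care groups". Of the 30% it says "This estimate of 30-day follow-up is taken directly from recent administrative data from Alberta", with no split between visits already arranged and visits newly made.

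The Outcomes section defines the endpoint more narrowly by purpose (a visit to review COPD management and deal with matters raised in the Alert) and more widely by time (90 days).

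No section mentions an appointment that existed before randomisation. The baseline items are in Appendix 6 and the follow-up questions in Appendix 7. Neither is in the text available for this review.

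**The concern.** Every enrolled patient has a PCP and a COPD diagnosis, so some will probably have a visit in the diary when they reach the ED. The Alert is faxed after randomisation and cannot have caused such a booking. Booked patients are likely to be seen in either arm, so they say little about whether the Alert prompts a visit. A chance difference between arms in the number booked feeds straight into the observed difference in follow-up.

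This information can be had before allocation at almost no cost. The named covariates do not stand in for it, since the plan presents them as influences on relapse and names none as a predictor of seeing a PCP. At stake is precision in a trial of about 49 analysed patients per arm, and how directly the result answers the plan's own question.

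**Working it through.** **Inputs from the plan.** Rates 30% v 60%, alpha 0.05, power 0.80 and 49 per arm (Sample Size Considerations). Allocation: "Randomization will be in a 1:1 distribution between the control and intervention group".

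**Assumptions, not in the documents.** Share already booked, q: 5% to 20%. Attendance at a booked visit, a: 80% to 95%, equal in both arms.

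**The plan's own figure.** Two-sided, with mean rate 0.45: n = [1.960 × √(2 × 0.45 × 0.55) + 0.842 × √(0.21 + 0.24)]² / 0.30² = 42 per arm. The continuity correction raises this to 49, or 98 in total. Then 49/0.9 = 54.4, so 55 per arm and 110 in total, as stated. The text says "we used 1-tailed estimates due to the assumption", but a one-tailed test gives 33 per arm, or 40 with the correction. Since 98 is reproduced only as two-sided, power below is two-sided. Crude power at 49 per arm is 85.9% by normal approximation and about 86.5% by simulation.

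**Size of the noise (q = 15%, a = 95%).** The SD of the between-arm difference in the share booked is √(2 × 0.15 × 0.85 / 49) = 0.072. The gap in follow-up between booked and unbooked patients is about 0.95 − 0.36 = 0.59. One SD of imbalance moves the primary difference by 7.2 × 0.59 ≈ 4 points.

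**Case A: overall rates stay at 30% v 60%, bookings included.** The unbooked rates are (0.30 − qa)/(1 − q) and (0.60 − qa)/(1 − q). At q = 15% and a = 95% these are 0.1575/0.85 = 18.5% and 0.4575/0.85 = 53.8%. For the Mantel-Haenszel test at these values:

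- expected score: (49 × 0.85/2) × 0.353 = 7.35
- null variance: 20.825 × 0.362 × 0.638 + 3.675 × 0.95 × 0.05 = 4.98
- variance under the alternative: 10.41 × (0.185 × 0.815 + 0.538 × 0.462) + 3.675 × 0.0475 = 4.33
- power: Φ[(7.35 − 1.96 × √4.98)/√4.33] = Φ(1.43) ≈ 92%

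Simulation agrees, with type I error about 5%. Over the assumed range:

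| Booked | Crude | Stratified (a = 80% to 95%) |
|---|---|---|
| 5% | about 86.5% | 87-88% |
| 10% | about 86.5% | 88-90% |
| 15% | about 86.5% | 89-92% |
| 20% | about 86.5% | 90-95% |

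**Case B: 30% v 60% holds only among unbooked patients.** The overall difference shrinks to 30 × (1 − q): 27 points at 10% booked and 24 at 20%. Crude power is about 78% and 68%. Stratifying gives 79-81% and 71-75%. Most of the loss is dilution, which stratification does not undo.

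**The case against.** The strongest reply is that nothing here is wrong. Allocation is concealed and 1:1, so bookings balance in expectation. The unadjusted test is valid, its error rate already covers chance imbalance, and in Case A it exceeds the planned 80% power. All of that stands. A reader might infer bias or an invalid primary test, and the documents support neither.

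A reader might also infer that every booked visit counts as a success whatever the Alert does. That goes too far. The Outcomes definition requires a COPD review, so a booked visit for another reason need not qualify. The Alert could affect attendance, or turn a routine visit into the review that counts. This is why booked patients should be stratified and not excluded.

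Third, the administrative 30% may already contain booked visits, in which case the sample size allows for them. The plan does not say. Case A then applies, and stratifying is an extra gain rather than a repair.

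Fourth, a booking item may exist in Appendix 6 or 7, and the covariate list is open-ended. That is possible. Only the analysis sentence would then need changing.

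Fifth, the remedy has costs. With 98 patients and 95% attendance, the chance that no booked patient misses the visit is (1 − 0.05q)^98, about 78%, 61%, 48% and 37% at 5%, 10%, 15% and 20% booked. An ordinary logistic booking term then has no finite estimate, although the treatment term does. The question may also prompt some patients to book. Doing so in both arms can raise control follow-up and shrink the contrast. This effect should be small, because both arms are already told to see their PCP.

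**Conclusion.** This is a cheap improvement, and the plan is not defective without it. In the available text the primary comparison uses no predictor of PCP follow-up, and an existing booking is a plausible strong one that can be known before allocation.

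At 5-10% booked the Case A gain is about 0.5 to 3.5 points of power (86.5% to between 87% and 90%). It reaches about 3.5 to 8.5 points at 20% booked (86.5% to 90-95%). In Case B power falls below 80% at 10% booked and stratifying recovers only part. That is not evidence that the trial is underpowered, because nothing in the documents says the 30% excludes booked visits. The booked share and attendance are assumptions throughout, and the figures apply to a 30-day window.

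Two matters in the same text weigh more and need settling first: the chi-square sentence names relapse instead of PCP follow-up, and the window is 30 days in the statistics sections but 90 in Outcomes.

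**What to change.** 1. Reconcile the 30-day and 90-day windows, and state that the principal analysis is of PCP follow-up.
2. Before allocation, record for every patient whether a PCP visit within that window is already booked (yes/no). For after-hours patients, ask in the next-morning call, before randomisation.
3. Test PCP follow-up with a Mantel-Haenszel chi-square stratified by that item, keeping all patients in.
4. Include the item as a prespecified term in the logistic model for PCP follow-up, in place of the relapse covariates. Use a penalised or exact fit if all booked patients attend.
5. Report the between-arm difference in patients without a booking as a supportive result.

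The cost is one baseline question and a short edit to the analysis section, with no change to the sample size. The downside is the possible reminder effect, which precedes allocation and so falls on both arms.
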